#### 2-week (±3 days) Compliance Phone Contact

Approximately 2 weeks after the baseline visit, study personnel will contact each subject by phone. Study personnel will reinforce the product use instructions and study instructions and will remind the subject of the 6-week visit.

#### 6-Week Visit (± 7 Days) & 3-Month Visit (± 7 Days)

Subjects will report to the study site with their dentifrice, toothbrush, diary and timer, having refrained from all oral hygiene procedures that morning and from eating, drinking and smoking for approximately 4 hours prior to their appointment time. Their medical history, current medication usage and inclusion/exclusion criteria will be updated and recorded. The dentifrice products will be weighed to assess product use and the diary entries will be reviewed to determine compliance with study requirements. The subject will be questioned about dentifrice use compliance by asking "Your brushing schedule is twice daily (morning and evening), for 1 minute per brushing, using only the toothpaste and toothbrush provided by All Sum Research. Have you deviated from that schedule at all?" (e.g. made any changes or forgotten to use the toothpaste). A "yes" or "no" answer to the question must be obtained. For all "yes" answers, the study site staff must determine what changed. Subjects will be assessed for any AEs they may have experienced since the previous visit.

The subjects will provide a post-baseline sensory evaluation. They will be asked if they have experienced any problems such as burning, stinging, irritation, etc., and, if so, the nature of the effect, severity and onset time (if known) will be recorded. A qualified dental examiner will perform an oral soft and hard tissue examination (OST), followed by gingival, bleeding, and plaque assessments.

The subjects will be provided with one additional tube of toothpaste.

The subjects will be reminded not to use any other oral hygiene products for the duration of the study. Subjects will be scheduled for their next visit and will be instructed to refrain from any oral hygiene procedures the morning of their next visit and to refrain from eating, drinking and smoking for approximately 4 hours prior to their next visit. They will be advised to follow the instructions carefully and return to the study site with their assigned toothpaste, toothbrush, timer and diary for their next appointment. Subjects will be scheduled for their next visit and will receive a reminder call prior to the visit.

#### 18-Week Compliance Visit (±7 Days)

At Week 18, subjects will report to the study site with their dentifrice, toothbrush, diary and timer for a compliance visit. Products will be weighed and diaries will be reviewed. Subjects will provide a sensory evaluation as described at the 6-week visit. The subjects will be provided with one additional tube of toothpaste.

The subject will be questioned about dentifrice use compliance by asking "Your brushing schedule is twice daily (morning and evening), for 1 minute per brushing, using only the toothpaste and toothbrush provided by All Sum Research. Have you deviated from that schedule at all?" (e.g. made any changes or forgotten to use the toothpaste). A "yes" or "no" answer to the question must be obtained. For all "yes" answers, the study site staff must determine what changed. Subjects will be assessed for any AEs they may have experienced since the previous visit and any changes to inclusion/exclusion criteria or medical updates.

The subjects will be reminded not to use any other oral hygiene products for the duration of the study. Subjects will be scheduled for their next visit and will be instructed to refrain from any oral hygiene procedures the morning of their next visit and to refrain from eating, drinking and smoking for approximately 4 hours prior to their visit. They will be advised to follow the instructions carefully and return to the study site with their assigned toothpaste, toothbrush, timer and diary at their next appointment. The study personnel will reinforce the product use instructions and study instructions and will schedule subjects for the 6-month visit. Subjects will receive a reminder call prior to their next visit.

#### 6-Month (± 7 Days)

Subjects will report to the study site with their dentifrice, toothbrush, diary and timer, having refrained from all oral hygiene procedures that morning and refraining from eating, drinking and smoking for approximately 4 hours prior to their appointment time. Their medical history, current medication usage and inclusion/exclusion criteria will be updated and recorded.

Subjects will provide a sensory evaluation as described at the 6-week visit. A qualified dental examiner will perform an oral soft and hard tissue examination (OST), followed by a gingival, bleeding and plaque assessments.

The subject will be questioned about dentifrice use compliance by asking "Your brushing schedule is twice daily (morning and evening), for 1 minute per brushing, using only the toothpaste and toothbrush provided by All Sum Research. Have you deviated from that schedule at all?" (e.g. made any changes or forgotten to use the toothpaste). A "yes" or "no" answer to the question must be obtained. For all "yes" answers, the study site staff must determine what changed. Subjects will be assessed for any AEs they may have experienced since the previous visit.

The dentifrice products will be weighed to assess product use and the diary entries will be reviewed to determine compliance with study requirements. All test products will be collected.

At the 6-month visit, subjects will complete a product questionnaire for informational purposes. This visit completes the subjects' participation in the study.

#### XI. STUDY ASSESSMENTS

A qualified examiner will evaluate the oral soft and hard tissues, gingival index (MGI), bleeding index (GBI) and plaque index (PI) (Soparkar Modified Turesky) for all subjects at all visits except the 18-week compliance visit. The examiner will be blinded to the treatment randomization assignments.

#### **Oral Soft and Hard Tissue Examination**

At each evaluation visit an examination of the oral hard and soft tissues will be conducted. Examination of the oral cavity will include lips, tongue, gingiva, sublingual area, buccal mucosa, muco-buccal and muco-labial folds, hard and soft palate, and pharyngeal area and cervical areas of all teeth. Assessments are to include color, texture, soft tissue abrasion, and any irregularities. Any effects and changes from the baseline will be recorded.

#### **Sensory Evaluation**

At all visits, the subjects will be asked if they have experienced any problems with their product during the study and the response will be recorded for safety purposes. If the subjects experience any effects such as burning, stinging, irritation, etc., the effect and severity and duration (if known) will be recorded. (At the baseline visit, subjects will be asked if they are currently experiencing any of the effects listed above.)

Clinical efficacy assessments will be performed by a single examiner at Baseline, 6 weeks and 3 and 6 months in the following sequence: MGI, GBI, PI.

#### **Gingival Inflammation (MGI)**

Gingival inflammation will be assessed at each evaluation visit, according to the Modified Gingival Index (MGI), and will be scored on buccal and lingual marginal gingivae and interdental papillae (four gingival areas: buccal, mesiobuccal, lingual and mesiolingual) of all scorable teeth using a scale of 0-4 as noted below:

- 0 = Normal (absence of inflammation).
- 1 = Mild inflammation (slight change in color, little change in texture) of any portion of the entire gingival
- 2 = Mild inflammation of the entire gingival unit.
- 3 = Moderate inflammation (moderate glazing, redness, edema, and/or hypertrophy) of the gingival unit.
- 4 = Severe inflammation (marked redness and edema/hypertrophy, spontaneous bleeding, or ulceration) of the gingival unit.

Whole mouth MGI scores will be calculated by summing all scores and dividing by the number of scorable sites examined.

#### **Gingival Bleeding Index (GBI)**

Gingival bleeding tendency will be assessed at each evaluation visit according to the Bleeding Index (BI) described by Saxton and van der Ouderaa. The gingiva will be lightly air-dried and a periodontal probe with a 0.5 mm diameter tip will be inserted into the gingival crevice to a depth of approximately 1 mm. The probe will be moved gently around the tooth at an angle of approximately 60 degrees to the long axis of the tooth, stroking the inner surface of the sulcular epithelium. Each of four gingival areas (distobuccal, midbuccal, mesiolingual, and midlingual) of the scorable

teeth will be probed in a likewise manner, waiting approximately 30 seconds before recording the number of gingival units which bleed, according to the following scale:

- 0 = absence of bleeding after 30 seconds;
- 1 = bleeding observed after 30 seconds; and
- 2 = immediate bleeding observed.

#### Soparkar Modification of the Turesky Modified Quigley-Hein Plaque Index (PI)

Plaque will be scored at each evaluation visit using the Soparkar modification of the Turesky Modification of the Quigley-Hein Plaque Index (PI), on all scorable buccal and lingual surfaces. Plaque is first stained with a disclosant and scored according to a 6-point interval scale in which the higher value denotes a quantitative increase in plaque.

Each tooth is visually divided into 6 areas for scoring: 1) mesio-facial, 2) mid-facial, 3) disto-facial, 4) mesio-lingual, 5) mid-lingual, and 6) disto-lingual. Thus, the maximum score per tooth is 30.

Plaque is quantified according to the following criteria:

0=No visible plaque

- 1=Separate flecks of plaque at the cervical margin of the tooth
- 2=A thin, continuous band of plaque (up to 1mm wide) at the cervical margin
- 3=A band of plaque wider than 1mm but covering less than one-third of the crown
- 4=Plaque covering at least one-third but less than two-thirds of the crown.
- 5=Plaque covering two-thirds or more of the crown.

A plaque index score for each subject is calculated by adding all the individual plaque scores (six per tooth), and dividing this sum by the total number of measurements.

#### XII. ADVERSE EXPERIENCES

#### **Adverse Event Definition and Handling**

An adverse event (AE) is any unexpected or serious medical occurrence in a clinical investigation subject during the study, whether or not related to the study product. An AE is therefore any unfavorable and unintended sign (including an abnormal laboratory finding), symptom or disease temporally associated with the administration of an investigational product, whether or not related to that investigational product. An unexpected AE is one of a type not identified in nature, severity, or frequency in the investigational product summary.

Adverse events will be reported to the sponsor within 24 hours and the sponsor will be notified immediately of any serious adverse event.

All adverse events observed by the Investigator and/or reported by the subject will be recorded throughout the entire study and documented. The Investigator will be asked to make a judgment on all adverse events as to their severity and possible relation to the study treatments.

More specifically, adverse events would include:

- Any unexpected event not seen before study initiation.
- Any pre-existing event that recurs with increased intensity or increased frequency subsequent to initial product treatment.

All adverse events should be recorded on the appropriate case report form, including date of onset, severity, duration, treatment and follow-up observation.

The following definitions will be used for grading severity of adverse events:

- Mild Either asymptomatic, or subject is aware of the sign, symptom or event, but it is easily tolerated.
- Moderate Discomfort enough to cause interference with usual activity and may warrant intervention.
- Severe Incapacitating with inability to do usual activities.

The Investigator will assess the likelihood that there is a reasonable possibility of a causal relationship between a study product and the adverse event. This will be captured using the following criteria: product related, non-product

related, non-product related but protocol related. The causal relationship to the product will be assessed as: definitely related, probably related, probably related, probably not related or definitely not related.

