#### STUDY OBJECTIVES

The objectives of this 6-month clinical research study are:

- 1) Primary objective is to evaluate the safety and efficacy of two baking soda dentifrices, containing 20% and 35% baking soda, (test products) compared to that of a non-baking soda dentifrice (negative control) in reducing gingival inflammation and bleeding.
- 2) Secondary objective is to evaluate the efficacy of two baking soda dentifrices compared to that of a non-baking soda dentifrice in reducing plaque.

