#### **Adverse Event Recording and Reporting**

All adverse events, whether serious or not, will be recorded on source documents and adverse event case report form. The recording period for all serious adverse events starts at the time the subject signs the informed consent. This includes events that emerge during screening. The recording period for a non-serious adverse event starts at the time the subject takes the first dose of study product. The recording period for serious adverse events lasts for 30 days and at least 7 days for non-serious adverse events after the subject's last administration of study product, regardless of relationship to the study product or protocol. The Investigator must follow up as medically necessary on all adverse events, serious adverse events, and other reportable events until the event has subsided or values have returned to baseline, or in the case of permanent impairment, until the condition stabilizes. For serious adverse events, the Investigator will provide all documentation pertaining to the event (*e.g.*, additional laboratory tests, consultation reports, discharge summaries, postmortem reports, etc.) to the Sponsor in a timely manner.

Information about all adverse events, serious and non-serious, including the event's severity, start and stop times/dates, chronicity, relatedness to study product, and any actions taken, must be recorded on the appropriate case report forms. The information recorded will be based on the signs and symptoms detected during the physical

examination and clinical evaluation of the subject as well as information recorded in the subject's diary, when applicable.

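### The adverse-event definition contradicts itself, so a new, non-serious effect already listed in the product summary may or may not count as an AE, depending on which sentence the site applies

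*Combined protocol and SAP*

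**What the plan says.** In the combined protocol and SAP, Section XII, Adverse Event Definition and Handling, four statements bear on what counts as an AE:

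- The opening sentence: "An adverse event (AE) is any unexpected or serious medical occurrence in a clinical investigation subject during the study".
- The second sentence: "An AE is therefore any unfavorable and unintended sign (including an abnormal laboratory finding), symptom or disease temporally associated with the administration". It refers to use of a study product and does not require the event to be related to it.
- The third sentence, on expectedness: "An unexpected AE is one of a type not identified in nature, severity, or frequency in the investigational product summary".
- A list of specifics with two entries: "Any unexpected event not seen before study initiation" and "Any pre-existing event that recurs with increased intensity or increased frequency subsequent to initial product treatment".

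The recording rule, under Adverse Event Recording and Reporting, is "All adverse events, whether serious or not, will be recorded on source documents and adverse event case report form".

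Safety is part of the leading aim of the trial. Study Objectives states: "Primary objective is to evaluate the safety and efficacy of two baking soda dentifrices", compared with a dentifrice without baking soda.

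Local effects also have a route of their own. Sections X and XI have subjects asked at every site visit about burning, stinging and irritation, with severity recorded, and have changes in oral tissues noted against baseline. Section XIV has the contract lab summarise tissue findings, sensory responses and AEs by product and time point. Its Safety Analysis includes tissue findings and subjective reports alongside AEs, and classifies adverse effects by intensity and by relationship to the product.

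**The concern.** The word joining the first two sentences is *therefore*, but the broad second sentence does not follow from the narrow first one. A site that works from the opening sentence and the list would leave expected, non-serious effects off the AE form. A site that works from the second sentence would enter them. The AE table by product would then depend on a choice that the protocol does not make and that a reader of the report could not reconstruct. Local irritation is the kind of effect that the protocol itself solicits for safety purposes, so the ambiguity could reach events that matter to the safety part of the primary objective.

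**Working it through.** No arithmetic applies: the point depends on no rate, effect size or sample size, and the plan states no figure to reproduce. The check sets the passages side by side.

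**Step 1. Apply each statement to four kinds of event.** Here *listed* means identified in the product summary in nature, severity and frequency, so that the event is not unexpected under the third sentence.

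| Event | First sentence | Second sentence | List of specifics |
|---|---|---|---|
| New, non-serious, not listed | AE | AE | AE |
| New, serious, listed | AE | AE | not covered |
| Pre-existing, recurs worse, non-serious, listed | not an AE | AE | AE |
| New, non-serious, listed | not an AE | AE | not covered |

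Only the last row falls outside both narrow statements and inside the broad one. The conflict is confined to that class. An event more severe or more frequent than the summary states is unexpected, and so remains an AE on every reading.

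**Step 2. See whether another rule settles it.** The recording rule removes any filter on seriousness. It does not remove the filter on expectedness, and it operates only once something already counts as an AE. The third sentence defines an unexpected AE as one type of AE. That presupposes expected AEs, which the first sentence excludes unless they are serious. No passage ranks the statements.

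**Step 3. List what an event in the last row receives if it is held only as a sensory response or tissue finding.**

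| Item | Sensory or tissue record | AE record |
|---|---|---|
| Occurrence | Yes (Sections X and XI) | Yes |
| Severity | Sensory: yes, but no scale defined. Tissue: effects and changes recorded, severity not named | Mild, moderate or severe, each defined in Section XII |
| Relationship to product | Not named as a recorded item | Investigator's judgment required |
| Follow-up until resolved or stable | Not stated | Required |
| Capture after last use | None stated after the 6-month visit | At least 7 days for non-serious events |
| Report to sponsor within 24 hours | Not stated | Required |
| Summary by product and time point | Yes (Section XIV) | Yes |

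**Step 4. Compare with what the analysis needs.** The Safety Analysis classifies adverse effects by relationship to the product. For an effect held only on the sensory or tissue record, no section provides for collecting that relationship. No section says when such a record must also become an AE. Section XII lets AE entries draw on examination findings and the diary, but gives no rule for doing so.

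**The case against.** A reader might infer that expected irritation disappears from the trial. The documents do not support that. Sensory effects are solicited at baseline, 6 weeks, 3 months, 18 weeks and 6 months with no condition on expectedness, tissue changes are recorded at each evaluation visit, and diaries take further effects. The Safety Analysis covers all effects that first appeared or grew worse after treatment began. Nor do sensory effects go without any severity: what they lack is a grade on the defined AE scale.

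A reader might also infer that AE rates will be understated. That depends on the product summary, which is not among the documents. If it lists no local effects, the narrow wording excludes none of them.

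The broad reading also has real support. The second sentence is framed as the conclusion, the third presupposes expected AEs, the mild grade extends to events without symptoms, and the list is introduced as what AEs would include, which can be read as illustration. A careful site could well apply the broad sentence. All of this stands, and it makes a loss uncertain. It does not remove the contradiction, because the first sentence and the first list entry still say otherwise.

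Finally, the Safety Analysis speaks of adverse effects, not adverse events, when it calls for relationship. That shows an intention to assess causality more widely, but no procedure collects it outside the AE form.

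**Conclusion.** The definition is internally inconsistent and should be corrected. The class affected is new, non-serious effects that the product summary lists at the severity and frequency seen. For these, the AE count, the relatedness judgment, the defined severity grade, AE follow-up and the 24-hour report all depend on which sentence the site applies. Occurrence by product remains available from the sensory and tissue summaries.

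The size cannot be computed, since no AE or irritation rate is given. It runs from no events, if the summary lists nothing relevant or the site uses the broad sentence, to every event in the class, if the site uses the narrow wording. The documents give no basis for saying that any shortfall would differ between arms. The efficacy analyses are not affected.

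**What to change.** Make four wording changes.

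1. In the opening sentence of Section XII, replace the unexpected-or-serious condition with *any untoward medical occurrence, whether or not expected or serious*. The condition must be replaced as a whole: striking only its first half would leave a definition limited to serious events.
2. In the first entry of the list of specifics, drop the word *unexpected*, so that it covers any new event.
3. Keep *unexpected* only as an attribute for reporting, as the third sentence already uses it.
4. State that a new or worsened sensory response or tissue finding that meets the definition is also entered as an AE, with a relatedness judgment.

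The cost is a few lines of text with the approvals that an amendment requires, plus more AE forms. Because Section XII asks for every AE to reach the sponsor within 24 hours, there will also be more such reports for mild events. Design, sample size and treatment are unchanged. If recording has already begun, the report should say which definition the site used.

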#### **Serious Adverse Event**

A serious adverse event is any adverse event that:

- Results in death.
- Is life threatening (i.e., immediate risk of death as the event occurred). A life-threatening event does not include an event that, had it occurred in a more severe form, might have caused death, but as it actually occurred did not create an immediate risk of death. For example, hepatitis that resolved without evidence of hepatic failure would not be considered life threatening even though hepatitis of a more severe nature can be fatal. Similarly, an allergic reaction resulting in angioedema of the face would not be life threatening, even though angioedema of the larynx, allergic bronchospasm, or anaphylaxis can be fatal.
- Results in persistent or significant disability or incapacity (i.e., a substantial, persistent disruption in a subject's ability to conduct normal life functions).
- Requires inpatient hospitalization or prolongation of an existing hospitalization (hospitalization is official admission to a hospital). Hospitalization or prolongation of a hospitalization constitutes criteria for an adverse event to be serious; however, it is not in itself considered a serious adverse event. In the absence of an adverse event, a hospitalization or prolongation of a hospitalization should not be reported as a serious adverse event by the participating Investigator. This is the case in the following situations:
  - The hospitalization or prolongation of hospitalization is needed for a procedure required by the protocol.
  - The hospitalization or prolongation of hospitalization is part of a routine procedure followed by the center (e.g., stent removal after surgery). This should be recorded in the study file.

In addition, a hospitalization for a pre-existing condition that has not worsened does not constitute a serious adverse event.

- Results in cancer.
- Results in a congenital anomaly or birth defect.

Additionally, important medical events that may not result in death, be life-threatening, or require hospitalization may be considered a serious adverse event when, based upon appropriate medical judgment, the event(s) may jeopardize the subject and may require medical or surgical intervention to prevent one of the outcomes listed in this definition. Examples of such medical events include: Allergic bronchospasm requiring intensive treatment in an emergency room or at home; blood dyscrasias or convulsions that do not result in hospitalization; or the development of drug dependency or drug abuse. If there is any doubt whether the adverse event constitutes a serious adverse event, the information will be treated as a serious adverse event.

